METHODS

Overview of Evaluation Methods

This evaluation will utilize a mixed methods approach. To evaluate our aims, the project will utilize a stepped wedge controlled trial design. This design staggers the timing of providing implementation support and allows every participating VISN to receive the implementation support. The unit of intervention in this study is the site and randomization will occur at the VISN level for virtual external facilitation. Using a balancing algorithm for facility size, suicide admissions, and rural vs. urban status, sites will be randomized to when virtual facilitation will occur. Below we describe the conceptual models, national implementation plan, clinical interventions, and implementation strategy, followed by the design, outcomes, and analysis for each specific aim.

Project Management

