The plan for national roll out of REACH VET was developed by OSP, with input from the evaluation team and other partners. National implementation of REACH VET began in November 2016 and included identification of a REACH VET coordinator at each facility, REACH VET dashboard training for coordinators and interested providers, and rollout of the dashboard. Each facility initially received the top eight names of patients identified as being in the top 0.1% of risk for suicide at that facility. Over the following three months, facilities will receive additional names via the dashboard until all patients in the top 0.1% have been identified; facilities can opt to receive the full list at any time. Standard implementation strategies will include training and education, chart note templates to support documentation, an intranet site of resources for coordinators and providers, technical assistance as requested, and clinical consultation as requested. Barriers and facilitators will be assessed during this time by the evaluation team.

Figure 2. Trial design.

		Study Month							
Network	Sites	1-3	3 – 6	6 - 9	9 - 12	12 - 15	15 - 18	18 - 21	21 - 24
A	1-4	Facilitation							
B	5-8	Awaiting Facilitation		Facilitation					
C	9-12	Awaiting Facilitation		Facilitation					
D	13-16	Awaiting Facilitation			Facilitation				
E	17-20	Awaiting Facilitation				Facilitation			
F	21-24	Awaiting Facilitation					Facilitation		
G	25-28	Awaiting Facilitation						Facilitation	

Virtual

External Facilitation Implementation Strategy

Additional implementation support will begin in April 2017. We will target 7 networks and 4 sites in each network not meeting the criterion for timely notification. The participating VISNs will be randomized to when the sites in their network will receive facilitation.

The facilitators will be two master’s level and one doctoral level clinicians with clinical expertise in suicide prevention and REACH VET; the facilitators are funded through OSP and are not part of the evaluation team. They attended facilitation training February 1-2, 2017. The training included how to conduct virtual facilitation and utilized a virtual external facilitation manual developed by a workgroup of the Behavioral Health QUERI’s Implementation Facilitation Learning Collaborative.

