Measures: Data sources will include qualitative interviews with site staff, including REACH VET coordinators, SPCs, mental health and primary care providers, and facility or VISN leadership. We will aim to conduct at least three interviews per facility, with a maximum of five interviews per facility. Interviews will be conducted by phone and be audio-recorded and transcribed. Interviews will be conducted to refine the virtual external facilitation strategies to be used. During virtual external facilitation, we will conduct monthly debriefings with the facilitators.

Analysis: Rapid Qualitative Analysis (RQA)³⁹ strategies will be used to ensure timely communication of findings to our OSP partners and to allow us to refine our virtual external facilitation strategies as needed. Each interview transcription will be read by two members of the qualitative team, who will then distill information pertaining to previously identified domains of interest based on iPARIHS (context, innovation, recipient), as well as emergent themes, into an episode profile. Episode profiles will be compared and any discrepancies resolved by referring back to the original transcript and/or presenting the profile to the larger team for discussion. Completed episode profiles will be entered into tables to create a composite matrix of data for each site, in order to be able to compare across participant responses. We will then share these episode profiles and site matrices with the qualitative coding team, REACH VET Program Manager, and external facilitators via a Lync meeting to discuss potential refinements to facilitation strategies.

Specific Aim 1b: Conduct a summative evaluation of virtual external facilitation versus standard implementation.

Design: All VA sites (N = 144) within VA's 18 regional networks that were directed to implement REACH VET will receive standard implementation. Network directors will be asked if they would like to receive additional implementation help for sites in their VISN having difficulty implementing REACH VET (e.g., not meeting the criterion of completing at least 80% of provider notifications of patient high-risk status within 7 days during the last month). VISNs participating will be randomized to when the VISN receives virtual external facilitation at 4 of their sites having difficulty implementing.

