| | | | | | | | | | | | | | | Post-Implementation | | | | | | | | | | | | |

Figure 1. Study design assuming stepped wedge method at VISN level.

After initial sensitivity analysis (see section on Model fitting) it was determined that clustering at the VISN level lacked sufficient sample size compared to the quasi-experimental pre-post design as represented in figure 2.

[figure not shown]

Figure 2. Study design timeline assuming clustering within site.

Model Fitting

Pan (2001) proposed a quaslikelihood model-selection method for GEE under the independence model criterion (QIC). This criterion can also be used to select the best working correlation structure in GEE analyses (Cui, 2007).

Stepped Wedge within *CLUSTERS* QIC Scores

| Outcome | Independent | Autoregressive | Compound Symmetry | Unstructured |
|---------------------------|-------------|----------------|-------------------|--------------|
| Coordinator Accepted | 59.0 | 60.0 | 69.2 | NC |
| Provider Assigned | 86.0 | 86.3 | 92.6 | 36.6 * |
| Care Evaluation Performed | 89.8 | 89.7 | 93.5 | 45.1 |
| Outreach Attempted | 95.3 | 95.5 | 126.8 | NC |

NC – non-convergence, * Unstructured matrix is predominately negative on the pairs

Stepped Wedge within *SITES* QIC Scores

| Outcome | Independent | Autoregressive | Compound Symmetry | Unstructured |
|----------------------|-------------|----------------|-------------------|--------------|
| Coordinator Accepted | 57.3 | 56.9 | 60.07 | CE |

| | | | | |
|---------------------------|-------|-------|-------|----|
| Provider Assigned | 97.1 | 92.0 | 109.2 | CE |
| Care Evaluation Performed | 109.0 | 102.8 | 116.6 | CE |
| Outreach Attempted | 116.9 | 107.8 | 119.8 | CE |

CE – converged with error

6-month Pre-Post within SITES QIC Scores

| Outcome | Independent | Autoregressive | Compound Symmetry | Unstructured |
|---------------------------|-------------|----------------|-------------------|--------------|
| Coordinator Accepted | 38.2 | 38.6 | 37.5 | NC |
| Provider Assigned | 73.0 | 66.5 | 57.0 | NC |
| Care Evaluation Performed | 80.7 | 73.0 | 71.8 | NC |
| Outreach Attempted | 87.2 | 81.3 | 81.6 | NC |

Choose 6-month pre-post quasi-experimental model using compound symmetry correlation structure for observations within sites, time variable in months to account for secular trends, and a binary intervention variable (0,1) indicating study phase (pre-facilitation, post-facilitation).

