Note, we do not model a transition period from pre-to-post Average number of implementation days = 175 (SD 49.3). Index date is based upon date of site visit.

Analysis

Our quasi-experimental pre-post intervention analysis evaluated four outcome measures as tracked by the REACH VET program across 23 VAMCs, during 6-month periods prior to implementation and again after the onset of implementation. We used the REACH VET Historic Summary Report to collect metrics for Coordinator assignment, Provider assignment, Care evaluation, and Attempted outreach all within one week of each monthly report's release date. To compare statistical differences in outcomes between pre-and post-periods we used generalized estimating equations (GEE) to control for clustering of observations within VAMCs. Fixed effects included a time-dependent variable identifying change in intervention status (pre-post) as well an independent variable of time to account for the possibility of improvement due to secular trends.

References

Cui, J. (2007). QIC Program and Model Selection in GEE Analyses. *The Stata Journal*:

Promoting Communications on Statistics and Stata, 7(2), 209–220.
<https://doi.org/10.1177/1536867X0700700205>

Pan, W. (2001). Akaike's information criterion in generalized estimating equations.
Biometrics, 57(1), 120–125. <https://doi.org/10.1111/j.0006-341x.2001.00120.x>

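### The SAP switches each site from pre to post at an undefined site visit, and no retained effect analysis uses the VISN's randomised start, so the phase effect may be biased in either direction.

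*SAP*

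**What the plan says.** The protocol fixes what is randomised under Overview of Evaluation Methods: "The unit of intervention in this study is the site and randomization will occur at the VISN level for virtual external facilitation". Specific Aim 1b, Design, repeats it: "VISNs participating will be randomized to when the VISN receives virtual external facilitation at 4 of their sites having difficulty implementing". Another sentence in the Overview speaks of the sites being randomised to timing. Read with the two statements above, the schedule is still set per VISN.

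The SAP sets aside its VISN-level stepped-wedge layout and chooses a site-level GEE with compound symmetry, a month term and a 0/1 phase term. Its Analysis section takes outcomes "during 6-month periods prior to implementation and again after the onset of implementation". The rule that places the break is in the closing note of Model Fitting: "Index date is based upon date of site visit". The same note says that no transition is modelled and that implementation lasted 175 days on average (SD 49.3).

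Three things are not stated:
- What a site visit is. The protocol calls the strategy virtual and never mentions one.
- Who set the visit date, and on what grounds.
- How the date relates to the VISN's randomised start.

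The stepped-wedge fits appear only as QIC scores, with no effect estimate retained from them. SAP Figure 2 (the site timeline) and the shading of Figure 1 were not available in the text reviewed. They might show site dates against VISN steps.

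**The concern.** The VISN's randomised start was fixed by design. A site visit comes later, and its date could respond to what is happening at the site. If sites were visited when a coordinator had just come into post, or just after a poor month, recovery unrelated to facilitation would fall at the pre/post break, and a linear month term would not absorb it. If facilitators were already working with a site before the visit, part of the effect would be counted as pre.

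The documents make both routes plausible without establishing either. The protocol's Conceptual Models section says that what facilitators do depends on the facility's needs and on where implementation stands. The SAP's Scope and Analysis section reports that two VISNs no longer needed facilitation when their turn came, which suggests that sites could improve while waiting. At stake is whether the estimated step can be attributed to facilitation.

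**Working it through.** **1. The plan's own count.** SAP Figure 1 lists clusters of 5, 4, 4, 6 and 4 sites: 5 + 4 + 4 + 6 + 4 = 23, as stated in the Analysis section. The documents give no effect size, variance or lag, so everything from step 3 on is illustration.

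**2. Window against length of implementation.** 175 / 30.44 = 5.7 months. If implementation starts at the visit, the 6-month post window is mostly the facilitation period itself.

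**3. Sensitivity of the step to its date.** Centre the 12 months at t = -5.5, ..., 5.5 and let p = 1 for t > 0. Least squares on month and phase stands in for the exchangeable GEE.
- The centred sums are S_tt = 143, S_pp = 3 and S_tp = 18, so phase and month correlate at 18 / √(143 × 3) = 0.87.
- Suppose the outcome rises by 10 points k months before or after the date used as the break. By symmetry both cases give S_yp = 5(6 - k) and S_yt = 5(36 - k²).
- Estimated step = [S_yp - (18/143) S_yt] / [3 - 18²/143], with denominator 0.734.

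| k (months) | Numerator | Estimated step (points) |
|---|---|---|
| 0 | 30 - 22.66 | 10.0 |
| 1 | 25 - 22.03 | 4.0 |
| 2 | 20 - 20.14 | -0.2 |
| 3 | 15 - 16.99 | -2.7 |
| 4 | 10 - 12.59 | -3.5 |

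The table can be read three ways:
- *A local gain unrelated to facilitation, with phase dated by the visit.* The false step is the full 10 points if the gain falls at the visit, but about zero or negative if it came 2 to 4 months before.
- *A real effect that began k months before the visit, with phase dated by the visit.* The effect is understated, and its sign reverses from k = 3.
- *A real effect that began at a visit k months after the randomised start, with phase dated by that start.* The same loss occurs. Averaged over delays of 0 to 3 months it leaves (10.0 + 4.0 - 0.2 - 2.7) / 4 = 2.8 points.

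**4. Simulation on the SAP's layout.** The layout is 23 sites in 5 VISNs with 6 months either side of the break. Assumed: monthly site SD 15 points, AR(1) correlation 0.3 or 0.6, trend 1 point per month, VISN starts 3 months apart, visit 0-1 or 0-3 months after the randomised start.

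| True effect | Date of the break | Mean estimate (points) |
|---|---|---|
| 0 | Randomised start | about -0.1 |
| 0 | Visit, lag unrelated to performance | about -0.1 |
| 0 | Visit in a good month or just after a bad one, 0-1 month range | +3.5 to +4.8 |
| 0 | Same, 0-3 month range | +7.3 to +9.4 |
| 10 | Visit, with facilitation running 1, 2 or 3 months earlier (correlation 0.6) | 4.0, -0.3, -2.6 |

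**The case against.** The strongest reply is that nothing in the documents shows visit dates departing from the randomised starts. The facilitators are external and funded by the operational partner, so visits could have been scheduled centrally, VISN by VISN. If visit and start coincide, the two datings give the same analysis. If the lag was unrelated to performance, no false gain arises. This stands. A reader might infer that visits were timed locally, or that the reported effect is inflated. The documents support neither.

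A second reply is that the SAP openly calls the analysis quasi-experimental. That discloses the loss of the randomised comparison in general. It does not say what event the visit is or how its date relates to the randomised schedule.

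A third reply is that dating by the randomised start has its own cost, and this also stands. With a linear month term, that fit can cancel or reverse a real effect that begins at a late visit, so a small estimate from it does not show that the visit-dated result was false. A reader might conclude that it should become the main estimate and would recover the randomised comparison. It would not: two VISNs are excluded for no longer needing facilitation, and the stepped-wedge model was dropped.

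**Conclusion.** The point holds as a conditional one. The only dating rule in the chosen model is an undefined visit after randomisation, the randomised quantity is VISN timing, and no retained effect estimate uses it. The SAP draws separate VISN-level and site-level timelines, which suggests that site dates need not equal the VISN step.

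Neither the size nor the direction of any bias can be determined from the documents. Under the assumptions shown, it runs from false gains of 3.5 to 9.4 points when visits follow performance, through none when the lag is unrelated to performance, to loss or reversal of a real 10-point effect when facilitation precedes the visit by 2 to 3 months. These ranges rest on the assumed variance, correlation and lags and are not estimates for this trial. What is firm is the fragility: phase and month correlate at 0.87 in a 12-month window, so moving the break by one or two months changes the answer materially.

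**What to change.** - Keep the visit-dated GEE and label it as-treated.
- Define the site visit, state who set its date, and say whether month is calendar time or time from index.
- Tabulate, by site, the lag from the VISN's randomised start month to the visit.
- Add a sensitivity analysis: the same site-level GEE, with phase and both 6-month windows set by the VISN's randomised start month for all its sites. State that it concerns switch timing in the analysed sites only.
- State that attribution to facilitation will be limited if the two estimates disagree, and read the disagreement against the lag table.

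The cost is SAP wording, one table and one more run on the same monthly reports. The downside is the loss shown in step 3 where visits were late. The pre window may also be short for the first VISN: if it started in April 2017 as the protocol planned, reports from November 2016 on give at most five earlier months (November to March).
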